5.3.5.2 Clinical Protocol

21. **Cycle 2+ Treatment: Angiosarcoma cohort 1** patients will be eligible for single-agent TRC105 until progression. At the time of progression by RECIST 1.1 on single-agent TRC105, patients will transition to treatment with the combination of TRC105 and pazopanib. **Angiosarcoma cohort 2** patients will be eligible for treatment with the combination until progression.
22. **Follow-up:** The follow-up visit should occur 28 days following the last dose of TRC105. The allowable visit window is +/- 7 days.
23. Allowable window for each visit within the cycle is +/- 2 days unless otherwise stated.

5.3.5.2 Clinical Protocol**5. SELECTION AND WITHDRAWAL OF PATIENTS**

For the Phase 1b dose levels -1, 1, 2 and expansion cohort 1, prior to administration of TRC105 on cycle 2 day 1, all study patients must maintain eligibility criteria indicating adequate organ function, medical status and ECOG performance status (i.e., all patients must maintain inclusion criterion #6, 8, 9 and 10 and exclusion criteria #8-21 to continue into cycle 2).

5.1. Patient Inclusion Criteria

1. Histologically confirmed unresectable soft tissue sarcoma (i.e., non-GIST, non-adipocytic) that has progressed following treatment with chemotherapy. Prior pazopanib is allowed if the drug was not discontinued for toxicity (Phase 1b only)
2. Histologically confirmed metastatic soft tissue sarcoma (i.e., non-GIST, non-adipocytic) that has progressed by RECIST following treatment with anthracycline chemotherapy. Patients may have received up to four lines of systemic therapy for metastatic disease and no more than two lines of combination treatment (Phase 2 only)
3. Histologically confirmed locally advanced (e.g. unresectable) or metastatic angiosarcoma that has progressed following treatment with prior systemic therapy. Progression must be documented on or following the most recent systemic therapy. Prior pazopanib is allowed if the drug was not discontinued for toxicity (Phase 2 angiosarcoma cohort only)
4. Measurable disease by RECIST
5. Age of 12 years or older (patient must weigh ≥ 40 kg)
6. ECOG performance status ≤ 1
7. Resolution of all acute adverse events resulting from prior cancer therapies to NCI CTCAE grade ≤ 1 or baseline (except alopecia or neuropathy)
8. Adequate organ function as defined by the following criteria:
 - Serum aspartate transaminase (AST; serum glutamic oxaloacetic transaminase [SGOT]) and serum alanine transaminase (ALT; serum glutamic pyruvic transaminase [SGPT]) ≤ 2.5 x upper limit of normal (ULN) or ≤ 5 x ULN in cases of liver metastases
 - Total serum bilirubin ≤ 1.5 times the upper limit of normal
 - Absolute neutrophil count (ANC) $\geq 1500/\mu\text{L}$
 - Platelets $\geq 100,000/\mu\text{L}$ without transfusion support within the past 28 days
 - Hemoglobin ≥ 9.0 g/dL without transfusion support within the past 14 days (erythropoietin or darbepoietin permitted)
 - Serum creatinine ≤ 1.5 times the upper limit of normal or creatinine clearance > 30 mL/min by Cockcroft-Gault formula
 - INR from 0.8 to 1.2

5.3.5.2 Clinical Protocol

9. Willingness and ability to consent for self to participate in study
10. Willingness and ability to comply with scheduled visits, treatment plan, laboratory tests, and other study procedures
11. Available archival tumor specimen of the soft tissue sarcoma that meets inclusion criterion #1, #2 or #3

5.2. Exclusion Criteria

1. Prior treatment with TRC105
2. Prior treatment with a VEGFR TKI (including pazopanib) (Part 2 only)
3. Current treatment on another therapeutic clinical trial
4. Receipt of systemic anticancer therapy, including investigational agents, within 28 days of starting study treatment. If anticancer therapy was given within 28 days of starting study treatment, patients may be included if 5 times the elimination half-life of the drug has passed.
5. No major surgical procedure or significant traumatic injury within 6 weeks prior to study registration, and must have fully recovered from any such procedure; date of surgery (if applicable) or the anticipated need for a major surgical procedure within the next six months. Note: the following are not considered to be major procedures and are permitted up to 7 days before therapy initiation: Thoracentesis, paracentesis, port placement, laparoscopy, thorascopy, tube thoracostomy, bronchoscopy, endoscopic ultrasonographic procedures, mediastinoscopy, skin biopsies, incisional biopsies, imaging-guided biopsy for diagnostic purposes, and routine dental procedures
6. Patients who have received wide field radiotherapy \leq 28 days (defined as $>$ 50% of volume of pelvic bones or equivalent) or limited field radiation for palliation $<$ 14 days prior to study registration or those patients who have not recovered adequately from side effects of such therapy
7. Uncontrolled chronic hypertension defined as systolic $>$ 150 or diastolic $>$ 90 despite optimal therapy (initiation or adjustment of BP medication prior to study entry is allowed provided that the average of 3 BP readings at a visit prior to enrollment is $<$ 150/90 mm Hg)
8. Significant ascites, pericardial or pleural effusion
9. History of brain involvement with cancer, spinal cord compression, or carcinomatous meningitis, or new evidence of brain or leptomeningeal disease. Patients with radiated or resected lesions are permitted, provided the lesions are fully treated and inactive, patients are asymptomatic, and no steroids have been administered for at least 28 days.
10. Angina, MI, symptomatic congestive heart failure, cerebrovascular accident, transient ischemic attack, arterial embolism, pulmonary embolism, PTCA or CABG within the past 6 months. Deep venous thrombosis within 6 months, unless the patient is anti-coagulated without the use of warfarin for at least 2 weeks. In this situation, low molecular weight heparin is preferred.

5.3.5.2 Clinical Protocol

11. Active bleeding or pathologic condition that carries a high risk of bleeding (e.g. hereditary hemorrhagic telangiectasia). Patients who have been uneventfully anti-coagulated with low molecular weight heparin are eligible.
12. Thrombolytic use (except to maintain i.v. catheters) within 10 days prior to first day of study therapy
13. Known active viral or nonviral hepatitis or cirrhosis
14. History of hemorrhage or hemoptysis (> ½ teaspoon bright red blood) within 3 months of starting study treatment
15. History of peptic ulcer within 3 months of treatment, unless treated for the condition and complete resolution has been documented by esophagogastroduodenoscopy (EGD) within 28 days of starting study treatment
16. History of gastrointestinal perforation or fistula in the past 6 months, or while previously on antiangiogenic therapy, unless underlying risk has been resolved (e.g., through surgical resection or repair)
17. Known human immunodeficiency virus (HIV) or acquired immunodeficiency syndrome (AIDS) related illness
18. Receipt of a strong CYP3A4 inducer within 12 days prior to cycle 1 day 1 or a strong CYP3A4 inhibitor within 7 days prior to cycle 1 day 1 ([Table 14](#))
19. Pregnancy or breastfeeding. Female patients must be surgically sterile (i.e.: hysterectomy) or be postmenopausal, or must agree to use effective contraception during the study and for 3 months following last dose of TRC105. All female patients of reproductive potential must have a negative pregnancy test (serum or urine) within 7 days prior to first dose. Male patients must be surgically sterile or must agree to use effective contraception during the study and for 3 months following last dose of TRC105. The definition of effective contraception will be based on the judgment of the Principal Investigator or a designated associate.
20. Other severe acute or chronic medical or psychiatric condition or laboratory abnormality that may increase the risk associated with study participation or may interfere with the interpretation of study results and, in the judgment of the Investigator, would make the patient inappropriate for this study

5.3. Patient Withdrawal Criteria

A patient should be withdrawn from study treatment if, in the opinion of the Investigator, it is medically necessary, or if it is the wish of the patient. If a patient does not return for a scheduled visit, every effort should be made to contact the patient. In any circumstance, every effort should be made to document patient outcome. Data to be collected at the end of study visit are described in the Schedule of Assessments ([Table 4](#), [Table 5](#), [Table 6](#) and [Table 7](#)). Patients will be followed for at least 28 days after the last dose of TRC105 study drug for adverse events. If the patient withdraws consent, no further evaluations should be performed, and no attempts should be made to collect additional data. In addition, patients will be withdrawn from treatment in the case of:

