5.3.5.2 Clinical Protocol

Schedule of Assessments Footnotes for Phase 1b Dose Levels 3, 4 and Expanded Cohort 2

1. **Days of Treatment with TRC105:** All assessments should be performed prior to the TRC105 infusion unless otherwise indicated. Each cycle is 28 days in duration.
2. **Cycle 1 day 1:** Hematology (including iron studies), blood chemistry (including TSH testing), urinalysis, physical examination, ECG and pregnancy test not required if acceptable screening assessment is performed within 7 days prior to the start of treatment on cycle 1 day 1.
3. **End of Study:** The end of study visit should generally occur within 14 days (+/- 1 day) of the last dose of TRC105. Assessments other than pharmacokinetics, immunogenicity and protein biomarkers do not need to be repeated if performed within the previous 2 weeks (previous 8 weeks for radiologic tumor assessments). Follow-up visits should occur 28 days following the last dose of TRC105 study drug as outlined in the Schedule of Assessments.
4. **Informed Consent:** Must be obtained prior to undergoing any study specific procedure and may occur prior to the 28-day screening period.
5. **Medical and Oncologic History, Demographics and Baseline Signs and Symptoms:** All information related to prior anticancer treatment should be recorded. Significant medical history and baseline signs and symptoms should be captured from the date of informed consent.
6. **Physical Examination:** Examination of major body systems and ECOG performance status.
7. **Vital Signs:** Heart rate, temperature, blood pressure, respiratory rate, weight. Assessment of vital signs during TRC105 Infusions: Vital signs are to be assessed pre-infusion (i.e., within 30 minutes of starting the infusion) every 30 minutes during the infusion (+/- 15 minutes) and at the end of the infusion (i.e. within 30 minutes after completing the infusion). Vital signs should be monitored more frequently and/or beyond the completion of the infusion if medically indicated (e.g. if the patient experiences an infusion reaction that has not yet resolved).

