5.3.5.2 Clinical Protocol

Schedule of Assessments Footnotes Phase 2 Soft Tissue Sarcoma

1. **Days of Treatment with TRC105:** All assessments should be performed prior to the TRC105 infusion unless otherwise indicated. Each cycle is 28 days in duration.
2. **Cycle 1 day 1:** Hematology (including iron studies), blood chemistry (including TSH testing), urinalysis, physical examination, ECG and pregnancy test not required if acceptable screening assessment is performed within 7 days prior to the start of treatment on cycle 1 day 1.
3. **End of Study:** The end of study visit should generally occur within 7 days (+/- 1 day) of the last dose of TRC105. Assessments other than pharmacokinetics, immunogenicity and protein biomarkers do not need to be repeated if performed within the previous 2 weeks (previous 8 weeks for radiologic tumor assessments). Follow-up visits should occur 28 days following the last dose of TRC105 study drug as outlined in the Schedule of Assessments.
4. **Informed Consent:** Must be obtained prior to undergoing any study specific procedure and may occur prior to the 28-day screening period.
5. **Medical and Oncologic History, Demographics and Baseline Signs and Symptoms:** All information related to prior anticancer treatment should be recorded. Significant medical history and baseline signs and symptoms should be captured from the date of informed consent.
6. **Physical Examination:** Examination of major body systems and ECOG performance status.
7. **Vital Signs:** Heart rate, temperature, blood pressure, respiratory rate, weight. Assessment during TRC105 Infusions: Vital signs are to be assessed pre-infusion (i.e., within 30 minutes of starting the infusion) every 30 minutes during the infusion (+/- 15 minutes) and at the end of the infusion (i.e. within 30 minutes after completing the infusion). Vital signs should be monitored more frequently and/or beyond the completion of the infusion if medically indicated (e.g. if the patient experiences an infusion reaction that has not yet resolved).

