18. **TRC105 and Pazopanib Pharmacokinetics Trough Concentration:** A 5 mL blood sample each for TRC105 and pazopanib pharmacokinetics to be collected at the time-points indicated in the Schedule of Assessments, prior to starting the TRC105 infusion and prior to pazopanib dosing. Samples will be stored at approximately -70°C. Samples will be batch shipped as indicated in the laboratory manual to a third-party laboratory. See separate laboratory guide for further collection and shipment information. Additional PK samples may also be collected at the time of unexpected clinical events.
19. **Protein Biomarkers:** One 10 mL purple top (K₃EDTA) tube will be collected at the time-points indicated in the schedule of assessments and stored at approximately -70°C to be analysed by a central laboratory. See separate laboratory guide for further collection and shipment information.
20. **Archival Tumor Tissue:** Archival specimens (formalin-fixed, paraffin-embedded) are required of the primary cancer and/or metastatic cancer specimen for each study participant. It is preferable that the entire paraffin block be submitted, but if this is not feasible, then at least 20 unstained slides are requested for immunohistochemical analysis (sections of 5 microns are preferred). See separate laboratory guide for further collection and shipment information.
21. **Cycle 2+ Treatment:** Patients who demonstrate a response of CR, PR or SD will be eligible for additional treatment until progression.
22. **Follow-up:** The follow-up visit should occur 28 days following the last dose of TRC105. The allowable visit window is +/- 7 days.
23. Allowable window for each visit within the cycle is +/- 2 days unless otherwise stated.

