5.3.5.2 Clinical Protocol

1. RECIST 1.1-defined disease progression. In cases where RECIST cannot be applied, progression should be based on unequivocal evidence of progressive disease sufficient to require a change in therapy. In the angiosarcoma cohort 1, disease progression for withdrawal refers to disease progression while receiving TRC105 plus pazopanib combination therapy.
2. A need for surgery, radiation, or for other anticancer therapy not specified in the protocol.
3. Unable to tolerate pazopanib during cycle 1 (phase 1b, dose levels -1, 1, 2 and expanded cohort 1 only).
4. Lost to follow-up or noncompliant.
5. Any TRC105 dose delay > 2 days between cycle 2 day 1 and cycle 2 day 28 (phase 1b only).
6. Pregnancy. Pregnant patients should be followed for the duration of the pregnancy and the outcome of the pregnancy should be documented.
7. Arterial thrombosis of any grade (including cerebrovascular ischemia, cardiac ischemia/infarction, or peripheral or visceral arterial ischemia) or grade 3 or 4 venous thrombosis (including pulmonary embolism).
8. Missed study drug treatment for > 8 consecutive weeks (i.e., both TRC105 and pazopanib dosing held). However, patients who cannot tolerate pazopanib or TRC105 therapy and who demonstrate a response of complete response (CR), partial response (PR) or stable disease (SD) with the combination and are thought to benefit from continued single agent therapy may continue on study on TRC105 or pazopanib alone.

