8.3.2. Adverse Event Reporting Period

Safety information for each patient will be collected from the date of informed consent. Adverse events occurring prior to the initiation of the study treatment with pazopanib or TRC105 study drug will be considered "baseline-signs and symptoms", will be recorded on corresponding case report forms and will not be retained for patients who fail screening. The adverse event reporting period for this trial begins when the patient has received even a portion of the first dose of pazopanib or TRC105 study drug and ends 28 days after the last dose of pazopanib or TRC105 study drug is administered.

All adverse events that occur in trial patients during the adverse event reporting period specified in the protocol must be reported to TRACON, whether or not the event is considered study treatment-related. In addition, any known untoward event that occurs beyond the adverse event reporting period that the Investigator assesses as possibly related to the investigational medication/product should also be reported as an adverse event.

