14.2. Retention of Records

To allow for appropriate evaluations and/or audits by regulatory authorities or TRACON, the Investigator agrees to keep records, including the identity of all participating patients (sufficient information to link records, CRFs and hospital records), all original signed informed consent forms, copies of all CRFs, source documents, and detailed records of treatment disposition. The Investigator should retain these records according to local regulations or as specified in the Clinical Trial Agreement, whichever is longer.

If the Investigator relocates, retires, or for any reason withdraws from the study, then TRACON should be prospectively notified. The study records must be transferred to an acceptable designee, such as another Investigator or another institution. The Investigator must inform TRACON of any such transfer of responsibilities and properly identify the person or institution assuming the responsibility. The responsible investigator/institution must obtain TRACON's written permission before disposing of any records.

5.3.5.2 Clinical Protocol**15. DEFINITION OF END OF TRIAL****15.1. End of Trial in all Participating Countries**

End of trial in all participating countries is defined as the time at which all patients enrolled in the study have completed treatment on study.

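### Closing safety visits are timed from the last TRC105 dose although patients may continue on pazopanib alone, so for longer continuers the 28-day visit falls during treatment

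*Combined protocol and SAP*

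**What the plan says.** **Continuation on one drug.** Section 5.3 (criterion 8), with matching text in sections 6.1.7 and 6.2.6, covers patients who cannot tolerate one of the drugs but have a response or stable disease on the combination. Those "thought to benefit from continued single agent therapy may continue on study on TRC105 or pazopanib alone".

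**Timing from TRC105 only.**
- Section 5.3: "Patients will be followed for at least 28 days after the last dose of TRC105 study drug for adverse events".
- Footnote 3 of Tables 4, 6 and 7: "The end of study visit should generally occur within 7 days (+/- 1 day) of the last dose of TRC105". Table 5 has the same rule with a longer interval: "The end of study visit should generally occur within 14 days (+/- 1 day) of the last dose of TRC105".
- Footnote 22 of Tables 4 to 7: "The follow-up visit should occur 28 days following the last dose of TRC105. The allowable visit window is +/- 7 days".
- Footnote 9 of Tables 4 to 7 places the post-treatment pregnancy test 28 days after the last TRC105 dose.

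**Timing from either drug.**
- Section 8.3.2: the adverse event reporting period "ends 28 days after the last dose of pazopanib or TRC105 study drug is administered".
- Footnote 16 of Tables 4 to 7 requires adverse event follow-up for at least 28 days after the last dose of TRC105 or pazopanib.

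**Partial exception.** In the angiosarcoma cohorts, Table 7 footnote 3 also calls for the end-of-study assessments when a patient permanently stops all study therapy. Its 28-day visit is still counted from TRC105.

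**The concern.** The plan allows a patient to outlast TRC105 on pazopanib and provides routes to that state. Table 10 leads to permanent discontinuation of TRC105 after repeated grade 3 or 4 toxicity, and Table 13 does so for severe infusion reactions. For such a patient the two closing visits, read literally, are counted from a dose that may lie weeks or months before treatment ends.

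This matters because section 8.3.1 has patients questioned about adverse events at clinic visits. A reporting period with no visit in it depends on what staff happen to observe and on what patients volunteer. The frequency and severity of adverse events is a phase 2 secondary objective (section 3.2.3), and the patients concerned have already failed to tolerate one component of the combination. The post-treatment pregnancy test moves with the same anchor. In Tables 4 and 6 no pregnancy test is scheduled between the start of treatment and that visit.

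**Working it through.** The plan gives no figure to reproduce. The check sets the anchors side by side and then does the date arithmetic.

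**Anchors**

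| Item | Source | Counted from last dose of |
|---|---|---|
| Adverse event follow-up, at least 28 days | Section 5.3 | TRC105 |
| End-of-study visit, 7 ± 1 days (14 ± 1 in Table 5) | Footnote 3, Tables 4–7 | TRC105 (Table 7 adds stopping all therapy) |
| Post-treatment pregnancy test, day 28 | Footnote 9, Tables 4–7 | TRC105 |
| 28-day visit, ± 7 days | Footnote 22, Tables 4–7 | TRC105 |
| Adverse event follow-up, at least 28 days | Footnote 16, Tables 4–7 | TRC105 or pazopanib |
| Adverse event reporting period, 28 days | Section 8.3.2 | pazopanib or TRC105 |

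**Date arithmetic.** Let T be the number of days from the last TRC105 dose to the last pazopanib dose. The documents do not give T, so it is an assumption shown over a range. Day 0 is the last TRC105 dose.

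- Follow-up visit: day V = 28, with window 28 − 7 = 21 to 28 + 7 = 35.
- End of the reporting period, reading section 8.3.2 as the later drug: day T + 28.
- Visit relative to the last pazopanib dose: V − T.
- Time from the visit to the end of the reporting period: (T + 28) − V, which equals T when V = 28.

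| T (days, assumed) | Day-28 visit relative to last pazopanib dose | Reporting period ends | Days from visit to end of period |
|---|---|---|---|
| 0 | 28 days after | day 28 | 0 |
| 14 | 14 days after | day 42 | 14 |
| 28 | same day | day 56 | 28 |
| 56 | 28 days before | day 84 | 56 |
| 112 | 84 days before | day 140 | 112 |

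The visit falls during treatment once T exceeds V: about 28 days, or 21 to 35 depending on where in the window it is held. The end-of-study visit falls during treatment sooner, once T exceeds 7 + 1 = 8 days (14 + 1 = 15 in Table 5). When T exceeds 35 days, both closing visits timed from TRC105 lie before the last pazopanib dose.

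**By schedule, for such a patient.** Tables 4, 5 and 6 leave no scheduled visit after the last pazopanib dose; Table 6 governs the 63-patient soft tissue sarcoma cohort. Table 7 leaves the end-of-study assessments, through its all-therapy trigger, but no 28-day visit.

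**Wording of the either-drug rule.** Neither section 8.3.2 nor footnote 16 says which last dose governs when the drugs stop on different days. Footnote 16 does contain a later-of clause, but it compares the 28 days with resolution of toxicity, not one drug with the other.

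**The case against.** The strongest reply is that safety follow-up does not stop. Footnote 16 in all four schedules and section 8.3.2 carry adverse event collection past the last pazopanib dose. Footnote 15 records concomitant medication to 28 days after the last study treatment. Section 8.3.9 follows events until they resolve or are judged chronic or stable. This stands. A reader might infer that no safety follow-up exists after the last study drug; the documents do not support that. What is missing is a scheduled visit, not the obligation.

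A second reply is that an end-of-study visit makes no sense for someone still on study, and footnote 3 says only that it should generally occur at the stated time. A sensible site might wait until all treatment ends. That is plausible, but footnote 22 has no such softening, and sites would have to depart from the written anchor to get it right. Section 6.1.7 keeps the assessment schedule running while TRC105 is held. Even if that extends to permanent discontinuation, it supplies on-treatment cycle visits and none after the last pazopanib dose.

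Three further inferences go too far:
- That every pazopanib-alone patient has the whole final 28 days without a visit. At T = 14 the visit falls 14 days after the last pazopanib dose, inside the reporting period.
- That the ± 7-day window, which permits a visit on day 21, loses a week of follow-up. It is a scheduling tolerance and does not shorten the period in section 8.3.2.
- That section 15.1, which ends the trial at "the time at which all patients enrolled in the study have completed treatment on study", cancels the last patient's follow-up. It is an administrative definition and releases no one from sections 8.3.2 or 8.3.9.

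**Conclusion.** The concern holds as an inconsistency of anchors with a practical consequence for a subset of patients. Section 5.3 and the visit footnotes count from TRC105, while footnote 16 and section 8.3.2 count from either drug. Followed literally, a patient on pazopanib alone for more than about 28 days (21 to 35 with the window) has the 28-day visit and its pregnancy test while still on treatment. Under Tables 4 to 6, once both closing visits have passed, nothing is scheduled after the last pazopanib dose; Table 7 retains the end-of-study assessments only.

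This rests on two assumptions: that the either-drug wording means the later drug, and that some patients continue on pazopanib alone for that long. The documents give neither the number of such patients nor their time on pazopanib alone, so the overall effect on adverse event rates cannot be sized. No sample size, power or error rate is affected. It is worth an amendment because a stated rule misplaces the visit and the correction is cheap.

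**What to change.** Reconcile the passages to one anchor.

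1. In section 5.3 and in footnotes 3, 9 (post-treatment pregnancy test) and 22 of Tables 4 to 7, count from the last dose of TRC105 or pazopanib, whichever is later.
2. In footnote 16 and section 8.3.2, add *whichever drug is stopped later*, so that the collection period and the visits share the same stated end. Re-timing the visits alone would leave these two passages ambiguous.
3. Keep the post-TRC105 pharmacokinetic and anti-product antibody samples timed from the last TRC105 dose.

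The cost is amendment wording. The number of closing visits is unchanged; for single-agent pazopanib continuers they move later. The small downside is that those patients' post-TRC105 samples would be separated from the closing visits and taken at a routine cycle visit.
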